3.2. Implementation of the N-CRM model

The purpose of this section is to define the proposed Neuenschwander's continual reassessment method (N-CRM) model for this study and to provide the details necessary to allow its implementation.

Where discrepancies exist between the text of this SAP and the study protocol document, the text in this SAP will prevail.

3.2.1. Candidate doses

The candidate doses to be considered are as follows:

Table 2 Candidate dose levels

| Candidate Dosing Level | DTX301 Dose (GC/kg) |
|------------------------|---------------------|
| 1 | 2×10^{12} |
| 2 | 6×10^{12} |
| 3 | 1×10^{13} |
| GC=genome copies | |

3.2.2. Definition of a Dose Limiting Toxicity

A dose limiting toxicity (DLT) is defined as any Adverse Event (AE), with a toxicity grade of three or higher ($AE \geq \text{Grade } 3$), that is considered related to the study drug by the investigator. As the N-CRM will be performed after 12 weeks of data have accrued for the last open cohort, only DLTs that occur within 12 weeks will be considered.

3.2.3. Definition of the Maximum Tolerated Dose

The estimate of the maximum tolerated dose (MTD) will be that dose with p(DLT) nearest to the target toxicity rate, regardless of whether or not the estimated p(DLT) is above or below the target toxicity rate.

3.2.4. Target toxicity rate

The target toxicity rate is 0.25. (*Nota Bene*: unlike the standard N-CRM model, this study will target a specific toxicity *rate* rather than a toxicity *band*.)

3.2.5. Escalation rule

The first cohort will receive 2×10^{12} GC/kg. A dose is cleared once a single cohort has been assessed at that dose. The maximum permitted dose escalation is 1 level relative to the highest cleared dose. Cohort 4 is not part of the cohorts included in the dose-escalation assessment as it is to be treated with the OBD defined with the assessment of the three previous dose cohorts.

3.2.6. N-CRM Stopping rules

The study will stop for success once results from six subjects treated at the current estimate of the MTD are available. Cohort 4 is not part of the assessment of the dose finding. The CRM model will recommend that the study is stopped for insufficient safety if the current estimate of the MTD is $< 2 \times 10^{12}$ GC/kg.

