3.2.8. Number of toxicities required before all doses are considered unsafe

The CRM model will not recommend stopping for insufficient safety until at least two DLTs have been observed. Note: this affects only the dose recommendation provided by the N-CRM model. It does not prevent an earlier termination based on clinical review of data emerging from the study.

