3.2.9. Cohort size

The cohort size will be three evaluable patients in every case for cohorts 1 to 3 as the expansion of cohort 3 and cohort 4 is not part of the N-CRM assessment. A patient is classed as evaluable if the patient remained in the study for at least 12 weeks after dosing or a DLT was observed within 12 weeks of dosing. Should a protocol amendment change the inclusion / exclusion criteria of the study for safety, then a decision will be taken and documented on which patients to include in the CRM model to recommend the next dose after the study resumes. The N-CRM model will not be modified to take into account any protocol amendment that may be developed after the first N-CRM model has been run.

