3.2.10. Other clarifications

- The N-CRM model will not contribute to the identification of the OBD. Estimation of the OBD will not influence the dose recommended by the CRM, but may be taken into account by the DMC when making the dosing decision for the next cohort.
- A DMC recommendation to administer a dose other than the three doses listed in section 3.2.1 above will be implemented only after a protocol amendment.

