9.7. Physical Examination Findings

Complete and targeted physical examination findings will be classified by investigator as Normal, Abnormal – Not Clinically Significant, and Abnormal – Clinically Significant. Shifts from baseline to each post-baseline time point will be presented by body system to show the number and percentage of subjects in each category for subjects in the SS.

10. Statistical Considerations for Data Monitoring Committee Meeting

DMC members will meet after data from Week 12 are available for all subjects in cohort 1, cohort 2 and the first 3 subjects in cohort 3. The decision to proceed to the next dose cohort, expand a dosing cohort, and enroll subjects to cohort 4 (Dosing Process Optimization) will be made after each DMC meeting. The DMC will also hold a meeting at completion of Week 52 for all subjects. Additional DMC meetings may take place, as needed. The full scope of each review will be outlined in the DMC charter.

11. Interim Analysis

An interim analysis may be conducted when week 12 data are available from all subjects from at least 2 dosing cohorts. All tables/listings/figures for the full analysis will be produced for the interim analysis. No interim analysis has taken place.

12. Changes from Analyses Planned in the Protocol

Table 15-1 (Schedule of Events – Outpatient and Inpatient Clinic Visits) in the protocol defines the study day prior to DTX301 dosing as Day 0. However, in accordance with Clinical Data Interchange Standards Consortium (CDISC) conventions, the study day prior to DTX301 dosing will be defined as study day -1.

Potential exploratory analyses of the time-normalized ammonia and/or percent of normal ureagenesis activity by gender has been added.

The DMC will not hold a meeting at completion of Week 12 for the first 3 subjects in cohort 4. It has been agreed to have it only at the completion of Week 52 for all subjects.

No interim analysis has taken place.

██ after patients in cohort 4 have completed the DLT window of 12 weeks or experienced a DLT prior to week 12 completion, in order to provide additional information for Health Canada submission. Patients from cohort 3 and 4 will be pooled together in the N-CRM model.

██ of AUC_{0-24h} of plasma ammonia and of $AUC_{0-240min}$ of absolute ^{13}C -urea vs. baseline have been added, along with other additional summary statistics for specific ureagenesis and ammonia parameters.

13. References

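### The model's stop for insufficient safety in SAP 3.2.6 cannot fire as worded, because the MTD estimate can never fall below the lowest candidate dose

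*SAP*

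**What the plan says.** Five parts of SAP 3.2 bear on this.

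- **3.2.1** introduces the dose set with "The candidate doses to be considered are as follows" and lists 2×10¹², 6×10¹² and 1×10¹³ GC/kg. Under 3.2.10, a DMC recommendation to "administer a dose other than the three doses listed in section 3.2.1 above will be implemented only after a protocol amendment".
- **3.2.3 and 3.2.4** set the target at 0.25 and define the MTD estimate as the dose with p(DLT) "nearest to the target toxicity rate, regardless of whether or not the estimated p(DLT) is above or below the target toxicity rate".
- **3.2.6, success:** "The study will stop for success once results from six subjects treated at the current estimate of the MTD are available".
- **3.2.6, safety:** "The CRM model will recommend that the study is stopped for insufficient safety if the current estimate of the MTD is" strictly below 2×10¹² GC/kg.
- **3.2.8**, whose heading is about when every dose is to be regarded as unsafe: "The CRM model will not recommend stopping for insufficient safety until at least two DLTs have been observed". It adds that this limits only the model's recommendation and leaves clinical review free to end the study sooner.

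SAP Section 12 adds a later model run for a Health Canada submission: "Patients from cohort 3 and 4 will be pooled together in the N-CRM model".

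**The concern.** A rule that picks the nearest of three listed doses can only return one of those three. The safety stop asks for something smaller than the smallest of them. The 3.2.8 heading and its two-DLT minimum show that the authors meant to have a working stop, so this is a decision rule that is wrong as written and not a detail left out.

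The success rule compounds it. With heavy toxicity at the lowest dose the MTD estimate stays at 2×10¹², and six subjects there satisfy the success condition whatever their outcomes. In the pooled run, a statement that the model recommended no safety stop would carry no information, yet a regulator could read it as reassurance.

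**Working it through.** **1. The logic.** MTD = the dose d in {2×10¹², 6×10¹², 1×10¹³} that minimises |p(d) − 0.25|. Its smallest possible value is 2×10¹². The condition MTD < 2×10¹² is therefore never true.

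**2. The rival reading.** If MTD meant a continuous dose solved from the fitted curve, it could fall below 2×10¹². But p(DLT) at that dose would equal 0.25 exactly, so choosing the nearest dose, and allowing for estimates above or below target, would have no meaning in 3.2.3.

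**3. The model.** Inputs from SAP 3.2.7: logit p = α + βx, x = ln(dose/6×10¹²); α has mean −2.3097 and SD 1.6604; log β has mean −0.4323 and SD 0.0044; ρ = −0.2405. I integrated the posterior on a grid with a binomial likelihood.

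The plan's own prior first. β ≈ exp(−0.4323) = 0.649. At 2×10¹², x = ln(1/3) = −1.099, so the logit is −2.3097 − 0.713 = −3.023 and the median p is 0.046. The other two medians are 0.090 and 0.121. The SAP tabulates 0.03, 0.06 and 0.12, so the fit is approximate at the two lower doses; the point does not depend on it.

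**4. Estimates at 2×10¹².**

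| DLTs / subjects | Posterior mean (median) p(DLT) | P(p > 0.25) | MTD by 3.2.3 |
|---|---|---|---|
| 2/3 | 0.376 (0.355) | 0.69 | 2×10¹² |
| 3/3 | 0.584 (0.599) | 0.935 | 2×10¹² |
| 6/6 | 0.743 (0.766) | 0.998 | 2×10¹² |
| 9/9 over 3/3/3 | 0.748 (0.768) | not given | 2×10¹² |

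SAP 3.2.7 also writes the slope SD with a log in front. Read as exp(0.0044) = 1.004, it gives 0.623 at 3/3 and 0.768 at 6/6, with the same MTD.

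**5. The success rule.** After 2 or 3 DLTs in Cohort 1 the model stays at 2×10¹². Any second cohort there gives a total between 2/6 (mean 0.234) and 6/6 (0.743). The MTD stays at 2×10¹² with six subjects, so the success rule is met; at 6/6 the estimate is 0.743/0.25, about 3 times the target. This is not universal: 0/3 at the low dose, 2/3 at the middle dose and then 0/3 at the low dose gives means 0.146, 0.248 and 0.307, and the MTD becomes 6×10¹².

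**6. How often, on the model alone.** Exact enumeration of up to three cohorts of 3, one-level escalation cap, success rule applied, final dose no higher than the highest tried, no DMC or protocol 3.2.7 action. The reworded rule (see the fix) is checked before the success rule. True rates are assumptions, except that the first row uses the SAP's tabulated prior medians. Results are on posterior means, with medians in brackets.

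| True rates | Safety stop as written | Safety stop reworded |
|---|---|---|
| 0.03/0.06/0.12 | 0% | 0.4% (0.4%) |
| 0.10/0.25/0.40 | 0% | 11% (11%) |
| 0.25/0.35/0.45 | 0% | 37% (37%) |
| 0.40/0.55/0.65 | 0% | 75% (77%) |

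At 0.40/0.55/0.65 the rule as written names 2×10¹² in 85% (80%) of runs and ends in success there with estimated p(DLT) above 0.25 in 61% (53%). At 0.03/0.06/0.12 that last figure is 0.04%. In every row the reworded stop replaces only runs that would have named 2×10¹²; selection of the two higher doses is unchanged (1×10¹³ stays at 96% in the first row). With slope SD 1.004, the reworded stop in the last row is 69% (73%). With the success rule checked first and the printed SD, it is 67% (77%).

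**7. The pooled run.** I assume 3/3/5 subjects: 9 enrolled at Amendment 5 (protocol 15.3.5) plus 2 in Cohort 4 (SAP 3.1). With the printed slope SD, the reworded rule needs 5 DLTs in 11 on means (0.254) or 6 on medians (0.311).

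**The case against.** The strongest case is about consequence. Protocol 3.2.7 stops enrollment at any event of Grade 3 or higher other than a hyperammonemic crisis, related or not, and restarting needs a substantial amendment approved by the regulator. A DLT is a related event of Grade 3 or higher, so the first one, unless it is such a crisis, halts the study before the model's two-DLT minimum is reached. Two toxic cohorts ending in success would need repeated approved restarts. All of this stands, and the 61% and 75% describe the model in isolation.

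Two stronger readings are therefore unsupported. A reader might infer that two cohorts at 2×10¹² always end in success; the path in step 5 refutes that. A reader might also infer that subjects lacked protection or that the choice of 1×10¹³ is undermined. The documents show independent stopping rules and DMC review, SAP 3.2.8 preserves termination on clinical review, and the defect concerns only runs that would name the lowest dose.

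Second, escalation is over and Cohort 4 closed after 2 patients (SAP 3.1), so no enrollment is left to stop. This is true, and it is why the criterion should be applied to the pooled run descriptively only.

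Third, the rewording is not free. SAP 3.2.3 accepts an MTD with estimated p(DLT) above target, and the reworded stop overrides this at the lowest dose after two DLTs, even at 0.254. That cost is stated under the fix.

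Fourth, the software description in SAP 4.11 is partly blacked out and the cited simulation report is not supplied, so the implemented setting is unseen. If the software interpolates a continuous dose, the SAP misdescribes it and still needs correcting.

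**Conclusion.** The point holds on the text: the stop for insufficient safety has probability zero under any data. This step needs no assumption beyond reading 3.2.3 as it is written. The size of the gap, 0% against 75% (77%) at assumed rates of 0.40/0.55/0.65, rests on the printed prior, cohorts of 3 and the model acting alone.

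The practical effect is limited to the pooled Health Canada run and an accurate account of the stopping rules in the report. Below 5 DLTs in 11 on posterior means, under the 3/3/5 assumption, even the pooled output would not change. The SAP should still be corrected, because a stated safety rule that cannot operate should not be reported as one that was applied and not met.

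**What to change.** Leave 3.2.3 as it is and replace the last sentence of 3.2.6 with:

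> Before the success rule is applied, the model will recommend stopping for insufficient safety if at least two DLTs have been observed and the posterior mean p(DLT) at 2×10¹² GC/kg exceeds 0.25.

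This is what an MTD below 2×10¹² means on the fitted curve. With all data at that dose it fires at 2/3 and 3/6 but not at 2/6, which agrees with the continuous-dose solutions: about 0.67–0.96×10¹², 0.82–1.03×10¹² and 2.3–3.1×10¹².

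In Section 12, state that the rule as worded during Cohorts 1 to 3 could not fire and that the reworded criterion is applied only descriptively to the pooled run. Report P(p(DLT) > 0.25) at each dose beside the recommended dose.

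SAP 3.2.9 is not breached. It says "The N-CRM model will not be modified to take into account any protocol amendment", and here the prior, the likelihood and the MTD rule all stay the same.

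**Cost.** One sentence in 3.2.6, one disclosure in Section 12, three probabilities, and no new data. The downside appears when the lowest dose is truly on target (0.25/0.35/0.45): an advisory stop in about 37% of model-only runs, with selection of 2×10¹² falling from 49% to 12% on means and from 40% to 3% on medians. The DMC can overrule the recommendation.

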3.2.7. Dose-toxicity model

The relationship between dose and toxicity will be modelled using logistic regression with median dose as the reference dose and pseudo-dose levels (the x-hats) defined as log(dose/reference). The minimum and maximum values for p(DLT) are 0 and 1 respectively.

Thus, we have

$$p(DLT|\hat{x}, \alpha, \beta) = \frac{e^{\alpha+\beta\hat{x}}}{1 + e^{\alpha+\beta\hat{x}}}$$

Where the joint prior for α and β is given by

$$\begin{pmatrix} \alpha \\ \log \beta \end{pmatrix} \sim N \left(\begin{pmatrix} \mu_\alpha \\ \mu_\beta \end{pmatrix}, \begin{pmatrix} \sigma_\alpha \times \sigma_\alpha & \sigma_\alpha \times \sigma_\beta \times \rho \\ \sigma_\alpha \times \sigma_\beta \times \rho & \sigma_\beta \times \sigma_\beta \end{pmatrix} \right)$$

Initial values for μ_α , μ_β , σ_α , σ_β and ρ are based on the following assumptions for the distribution of p(DLT) at each dose:

| Dose | 2.5% centile | Median (50% centile) | 97.5% centile |
|--------------------------|--------------|----------------------|---------------|
| 2x10 ¹² GC/kg | 0.006 | 0.03 | 0.65 |
| 6x10 ¹² GC/kg | 0.008 | 0.06 | 0.70 |
| 1x10 ¹³ GC/kg | 0.012 | 0.12 | 0.80 |

which lead to the following parameterization of the joint prior:

| Alpha | | Log(Beta) | | Rho |
|---------|--------|-----------|--------|---------|
| Mean | SD | Mean | SD | |
| -2.3097 | 1.6604 | -0.4323 | 0.0044 | -0.2405 |

Thus, we set $\mu_\alpha = -2.3097$, $\log \mu_\beta = -0.4323$, $\sigma_\alpha = 1.6604$, $\log \sigma_\beta = 0.0044$ and $\rho = -0.2405$.

Since the standard deviation (SD) of α is non-zero, the intercept is allowed to vary.

3.2.8. Number of toxicities required before all doses are considered unsafe

The CRM model will not recommend stopping for insufficient safety until at least two DLTs have been observed. Note: this affects only the dose recommendation provided by the N-CRM model. It does not prevent an earlier termination based on clinical review of data emerging from the study.

3.2.9. Cohort size

The cohort size will be three evaluable patients in every case for cohorts 1 to 3 as the expansion of cohort 3 and cohort 4 is not part of the N-CRM assessment. A patient is classed as evaluable if the patient remained in the study for at least 12 weeks after dosing or a DLT was observed within 12 weeks of dosing. Should a protocol amendment change the inclusion / exclusion criteria of the study for safety, then a decision will be taken and documented on which patients to include in the CRM model to recommend the next dose after the study resumes. The N-CRM model will not be modified to take into account any protocol amendment that may be developed after the first N-CRM model has been run.

3.2.10. Other clarifications

- The N-CRM model will not contribute to the identification of the OBD. Estimation of the OBD will not influence the dose recommended by the CRM, but may be taken into account by the DMC when making the dosing decision for the next cohort.
- A DMC recommendation to administer a dose other than the three doses listed in section 3.2.1 above will be implemented only after a protocol amendment.

3.3. Treatments

Subjects will receive a single, peripheral IV infusion of DTX301, administered by qualified study personnel as designated by the investigator. The dose will be determined by the cohort and candidate dose.

Subjects in cohort 4 will be treated with the OBD defined with the assessment of the three previous dose cohorts. Subjects treated in cohort 4 (Dosing Process Optimization) will utilize an alternative regimen of corticosteroids, aiming at prophylaxis of vector-induced hepatitis. Therefore, prednisone (or prednisolone) will be initiated before dosing with DTX301, sustained for 4 weeks, followed by tapering.

The dose of DTX301 to be administered will be calculated using the subject's weight recorded at Screening. The subject's weight will be verified prior to administration of DTX301 to ensure that their current weight is within 10% of their weight at Screening.

The efficacy data will be modeled by dose (i.e. cohorts 3 and 4 will be combined, with OBD being determined as 1.0×10^{13} GC/kg). The other data will be summarized/reported by DTX301 dose/prophylactic corticosteroids (i.e. by cohort) and presented in the tables, figures and listings as follows:

- DTX301 2.0×10^{12} GC/kg
- DTX301 6.0×10^{12} GC/kg
- DTX301 1.0×10^{13} GC/kg
- DTX301 1.0×10^{13} GC/kg + Prophylactic corticosteroids

4. General Statistical Considerations

